14 STATISTICAL ANALYSIS

A statistical analysis plan (SAP) will be prepared after the protocol is approved. This document will provide further details regarding the definition of analysis variables and analysis methodology to address all study objectives. The SAP will serve as a complement to the protocol and supersedes it in case of differences.

The statistical evaluation will be performed using SAS[®] software version 9.4 or higher (SAS Institute, Cary, NC). All data will be listed, and summary tables will be provided. Summary statistics will be presented by dose cohort. For continuous variables, data will be summarized with the number of patients (N), mean, standard deviation, median, minimum, and maximum by dose group. For categorical variables, data will be tabulated with the number and proportion of patients for each category by dose group.

14.1 Determination of Sample Size

Based on clinical experience, a total of up to 18 patients will be enrolled to achieve the study objectives in this study. Approximately 30 patients will need to be screened. The number of patients screened is based on a screen failure rate of 40%.

14.2 Analysis Populations

As-Treated Population

The as-treated population will include all patients who receive at least 1 dose of MT1002. All efficacy, safety, and pharmacodynamics data will be summarized in this population.

Pharmacokinetics Population

The PK population will include those patients in the as-treated population who have valid PK concentration data. PK concentrations and PK parameters will be summarized in this population.

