5.2.2 Secondary Endpoints

The secondary endpoints are as follows:

- MACE within 30 days
- AEs of interest: bleeding events, infusion reactions, hypersensitivity reactions, thrombotic events (including stent thrombosis), frequency of abrupt vessel closure (AVC), transient ischemic attack, redo of stent procedure (revascularization), or emergency coronary artery bypass grafting (CABG)
- Minor bleeding events (BARC Type 2)
- General AEs including change from baseline abnormal safety laboratory test results
- ACT, aPTT, PT, TT, FIB, INR
- PA and correlation with PK

- Thrombolysis in myocardial infarction (TIMI) flow
- Percentage of patients who achieve $ACT \geq 200$ sec
- PK of MT1002

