8.2 Dosage Schedule

Patients will receive MT1002 IV followed by MT1002 infusion for 4 hours. This regimen was found safe and well tolerated in Phase 1. MT1002 will be initiated as close to the start of PCI as possible. MT1002 should be initiated during diagnostics angiography when indication for PCI is confirmed, provided the early PCI is indicated right after the coronary angiography. PCI can start after MT1002 initiation as soon as ACT is confirmed to be ≥ 200 sec or within 30 min after MT1002 starts, whichever occurs first. MT1002 will be administered by an intravenous injection of 0.90 mg/kg, 1.2 mg/kg, 0.75 mg/kg or 0.6 mg/kg (depending on the dose selected for the cohort) via IV access prior to the PCI procedure, immediately followed by an IV infusion of 1.8 mg/kg/hour, 2.3 mg/kg/hour, 1.6 mg/kg/hour or 1.2 mg/kg/hour (depending on the dose selected for the cohort) until completion of the procedure.

Patients will be discharged from the hospital when they are stable, as defined by the Investigator's judgment. Patients will be followed for 30 days from study drug dosing.

Three doses of MT1002 will be evaluated in this study as noted in the table below. The first dose level is 0.90 mg/kg initial loading dose (bolus intravenous injection) + 1.8 mg/kg/h (infusion) for 4 hours. The second dose level will be based on the results from the first cohort (If the dose is escalated, then the second dose level is 1.2 mg/kg initial loading dose (bolus intravenous injection) + 2.3 mg/kg/h (infusion) for 4 hours; if the dose is de-escalated, then the second dose level is 0.6 mg/kg initial loading dose (bolus intravenous injection) + 1.2 mg/kg/h (infusion) for 4 hours). The third dose will be based on the results from the initial 2 cohorts (Table 3). The goal is to achieve a target ACT of 200 to 300 sec (within 30 minutes after infusion initiation) during the continuous infusion period of MT1002.

Patients who are enrolled but do not undergo PCI (e.g., because of PCI contraindication revealed after coronary angiography or due to exclusion criteria) will be replaced for the study. However, the patients will be evaluated as safety population.

Dose adjustment guideline for cohort 3 dosing regimen is below. All adjustment will be documented in the patient's source document in detail:

- Bolus and maintenance dosing

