All patients will receive 0.75 mg/kg as an IV bolus dose, followed immediately by 1.6 mg/kg/hr*4h IV for the duration of the PCI. Five minutes after the bolus dose, ACT should be performed and an additional bolus of 0.3 mg/kg IV may be given if needed (i.e., ACT <200 sec).

- Dosing during infusion period

10 minutes after initiation of 1.6 mg/kg/hr IV for the duration of the PCI, or 5 minutes after additional bolus if it is given, additional ACT can be monitored, and IP infusion rate can be adjusted. An incremental 10% additional infusion rate can be titrated up until ACT >200 sec. If ACT >300 sec during that period of time, IP infusion can be stopped for 5 minutes, and/or the rate of infusion can be adjusted until ACT maintains between 200 sec and 300 sec. Duration of IP infusion can be 4 hours +/-30 minutes in order to accommodate potential infusion rate adjustments.

Table 3 Planned Dose Regimen of MT1002 for Injection and Expected ACT and aPTT Values

Sequence	N	MT1002: Initial loading dose and maintenance dose	Expected peak ACT based on Phase 1 results in healthy volunteers	Expected peak aPTT based on Phase 1 results in healthy volunteers	Expected ACT in 5 min after MT1002 start	Expected aPTT in 5 min after MT1002 start	Expected ACT in 30 min after MT1002 start	Expected aPTT in 30 min after MT1002 start
First dose cohort	6	0.90 mg/kg + 1.8 mg/kg/h*4h	234.3±26.1 sec – at 4 hours	74.4±6.2 sec – at 4 hours	209.7±19.2	63±4.8	212.3±29.5	65.6±7.5
Second cohort if dose escalated	6	1.2 mg/kg + 2.3mg/kg/h*4h	253.8±9.6 sec – at 2 hours	83.6±5.4 sec – at 4 hours	234.3±6.9	74.5±7.3	240.3±4.1	78.3±9
Second cohort if dose de-escalated	6	0.60 mg/kg + 1.2 mg/kg/h*4h	221.7±11.1 sec – at 2 hours	65.9±2.5 sec – at 4 hours	194.5±28.6	56.5±7.4	216.2±15.7	60.6±4.4
Third expansion cohort	6-8	0.75 mg/kg + 1.6 mg/kg/h*4h based on results from initial 2 cohorts	220.7 sec at 4 hours	67.7 sec at 4 hours	217.5	66.5	216.5	66.1

Abbreviations: ACT, activated clotting time; aPTT, activated partial thromboplastin time; h, hours; min, minutes; N, number of patients; sec, seconds; Tbd, to be determined.

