14.3.2 Analysis of Pharmacodynamic Endpoints

The ACT, aPTT, PT, TT, FIB, INR will be summarized descriptively by visit, cohort, and overall.

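### Outside the co-primary definition, the plan does not separate results on MT1002 from results after rescue, nor cohort 3 success before dose adjustment from success after it

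*Combined protocol and SAP*

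**What the plan says.** **Population.** Section 14.2: "The as-treated population will include all patients who receive at least 1 dose of MT1002". It continues: "All efficacy, safety, and pharmacodynamics data will be summarized in this population". The only other population defined is for PK.

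**Grouping.** Section 14: "Summary statistics will be presented by dose cohort". Whether this means assigned or received dose is not stated.

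**Endpoints.** The co-primary endpoint in Section 5.2.1 requires target ACT on MT1002 without a switch to standard treatment, together with PCI success. Section 14.3.1 restates it without the no-switch condition. Section 5.2.2 lists "Percentage of patients who achieve" an ACT of at least 200 sec, with no on-drug condition and no time window. Section 14.3.2: "The ACT, aPTT, PT, TT, FIB, INR will be summarized descriptively by visit, cohort, and overall". Section 14.3.1 treats platelet aggregation (PA) in the same way.

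**Rescue and bail-out.** Sections 6.1 and 8.5.1 switch patients who miss the ACT target within 30 minutes to unfractionated heparin (UFH) or bivalirudin. Section 8.5.1 also allows bail-out with IIb/IIIa inhibitors or heparin.

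**Cohort 3 adjustment.** Section 8.2, for cohort 3 only: "an additional bolus of 0.3 mg/kg IV may be given if needed (i.e., ACT <200 sec"; and "An incremental 10% additional infusion rate can be titrated up until ACT >200 sec".

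**Patients without PCI.** Section 8.2 replaces them and adds: "However, the patients will be evaluated as safety population".

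**The concern.** The trial is meant to show what each MT1002 regimen does to clotting and platelets. Two kinds of value do not show that, and Section 14 has no rule for either.

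- **Values after another anticoagulant or antiplatelet drug.** Rescued patients stay in the as-treated set with all their later samples. Section 8.5.1 requires heparin wash-out before dosing because residual heparin could confound MT1002's effect on the coagulation indices. There is no matching rule once heparin is given as rescue.
- **Values after a cohort 3 top-up or rate increase.** These are still on MT1002 with no switch, so they count as success in every ACT endpoint, including the co-primary. Table 3 nevertheless lists cohort 3 as 0.75 mg/kg + 1.6 mg/kg/h with its own expected ACT. The Version 6.0 summary of changes says the adjustment guideline is there so that a regimen can be identified and confirmed for phase 3. A reader of the results could not tell how often the listed regimen was enough by itself.

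**Working it through.** **1. The plan's own figure.** 18/(1 − 0.40) = 30 patients screened. This reproduces Section 14.1 and is not in dispute. The study is descriptive, with no hypothesis test or power figure to check.

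**2. Which results rescue can reach.** Section 8.5.1 stops MT1002 30 minutes before UFH or a IIb/IIIa inhibitor, and at least 30 minutes before bivalirudin. If failure is declared at 30 minutes, rescue starts at about 30 + 30 = 60 minutes.

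| Result | Can it include values after rescue? |
|---|---|
| Co-primary (5.2.1) | No, switched patients are excluded by definition |
| 5-min and 0.5-h samples | Should precede rescue |
| Unscheduled ACTs during PCI | Yes |
| 4, 6, 8 and 24 h coagulation and PA samples | Yes |
| ACT of at least 200 sec (5.2.2) | Yes, no drug or time limit |

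**3. Cohort 3 dose arithmetic** (Table 3 and Section 8.2).

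- Bolus with top-up: 0.75 + 0.30 = 1.05 mg/kg. This is 0.30/0.75 = 40% above the listed bolus, and above cohort 1's 0.90.
- By 30 minutes: listed 0.75 + 1.6 × 0.5 = 1.55 mg/kg; with top-up 1.85; cohort 1 0.90 + 1.8 × 0.5 = 1.80.
- Over 4 h: listed 0.75 + 1.6 × 4 = 7.15 mg/kg; with top-up 7.45; cohort 1 0.90 + 1.8 × 4 = 8.10.
- Top-up plus one 10% step: the rate is 1.6 × 1.1 = 1.76 mg/kg/h, and the total is at most 1.05 + 1.76 × 4 = 8.09 mg/kg. That takes the step as held for all 4 h, which slightly overstates it.

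A top-up alone stays below cohort 1's 4-hour total. With one rate step the total comes close to it, still under the cohort 3 label.

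**4. Weight of one patient.** 1/6 = 16.7 points; 1/8 = 12.5 points (Table 3 allows 6 to 8 in cohort 3). If two of six successes came only after rescue or adjustment, 6/6 = 100% (exact 95% interval 54.1 to 100) becomes 4/6 = 66.7% (22.3 to 95.7).

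**5. How many patients?** Assume the Table 3 healthy-volunteer values are normal and ± is an SD, so P(ACT < 200) = Φ((200 − mean)/SD).

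- *Cohort 3 top-up at 5 minutes:* mean 217.5, no SD given. The other 5-minute SDs in Table 3 (6.9 to 28.6) give Φ(−17.5/6.9) = 0.006 up to Φ(−17.5/28.6) = 0.270, or 0.03 to 1.6 of 6.
- *Rescue at 0.90/1.8:* P(< 200) is Φ(−9.7/19.2) = 0.307 at 5 minutes and Φ(−12.3/29.5) = 0.338 at 30 minutes. Reaching target at either time avoids rescue. Being low at both is 0.307 × 0.338 = 0.10 if independent, and at most 0.31.
- *Rescue at 0.60/1.2:* 0.576 at 5 minutes and 0.151 at 30 minutes. Low at both is 0.576 × 0.151 = 0.09 if independent, and at most 0.15.

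The Version 6.0 summary of changes reports that all 6 cohort 1 patients reached target. These ranges are too wide, and too far from patient data, to serve as forecasts.

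**6. Two pairs of passages that do not agree.**

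- Section 8.2 and the Synopsis evaluate dosed patients without PCI as a safety population. Section 14.2 defines no such population and puts every dosed patient into efficacy. One such patient changes 6/6 to 6/7 (85.7%).
- For cohort 2, Table 1 counts patients whose peak ACT is below 200. The text below it counts patients with any ACT below 200. A patient with one low value and a later higher one meets the second but not the first. A value after rescue could raise the peak but could not erase the low reading.

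**The case against.** The strongest case against has four parts.

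- **Section 14 defers variable definitions to a SAP that supersedes the protocol, and all data will be listed.** True, and with up to 18 patients each case will be visible in listings. But no SAP text is in the document reviewed, and the deferral shows where the rule belongs. Listings do not correct a tabulated percentage.
- **Cohort 3 is an ACT-guided strategy, so success after a permitted adjustment is legitimate.** This stands for the strategy. It does not stand for the fixed regimen in Table 3, and the two should be separable under either reading. No cap on rate steps is stated, but titration ends once ACT exceeds 200 sec.
- **The Study Management Group would not count heparin values blindly.** Fair: it weighs safety, efficacy and drug concentration along with the criteria, and includes an independent cardiologist. That is why the Table 1 point is confined to reconciling wording.
- **Limiting efficacy to patients who undergo PCI would condition on an event after dosing.** Correct, so no such restriction is recommended.

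A reader might also infer that rescue ACT is credited in the co-primary. Section 5.2.1 rules that out. Nor does the text say that results are grouped by planned dose; it leaves assigned versus received open.

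**Conclusion.** The concern holds in a limited form. Read literally, Sections 14.2 to 14.3.2 with Section 5.2.2 let values under UFH, bivalirudin or IIb/IIIa bail-out enter the ACT ≥ 200 sec percentage and the later coagulation and PA summaries. They also leave cohort 3 success before and after adjustment unseparated, including in the co-primary.

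The size is 16.7 points per affected patient in a cohort of 6, which is exact arithmetic. The number affected is uncertain. A reader might equate the chance of a 30-minute ACT below 200 (15% to 34%) with the rescue rate and expect the secondary endpoint to drift to 100%. The documents do not support that: target can be reached earlier within the 30 minutes, all 6 cohort 1 patients reached it, and not every rescue need yield a recorded ACT of 200 sec.

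The timing conclusion assumes that failure is declared at 30 minutes and the stated gap is kept. In a descriptive study without hypothesis tests this should be fixed as a cheap improvement, but it does not undermine the trial.

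**What to change.** Analysis changes only, in the SAP or Section 14:

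1. Repeat the on-MT1002, no-switch condition in Section 14.3.1. Add it to the ACT ≥ 200 sec endpoint, counting switched patients as non-achievers unless they reached 200 sec before the switch.
2. Summarise coagulation and PA values up to any switch or bail-out, and list later values separately.
3. For cohort 3, report success before any adjustment, including the 5-minute ACT before a top-up, separately from success after adjustment, with the mg/kg each patient received.
4. State whether cohort summaries follow assigned or received dose.
5. Reconcile Section 8.2 and the Synopsis with Section 14.2 on dosed patients without PCI. Reconcile the two cohort 2 wordings in Section 6.1 and the Synopsis. Which wording should govern is for the sponsor to decide.

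The cost is small. Dose and time go into the eCRF (Section 8.4), as do ACT values after adjustment (Section 9.2.2). Section 8.2 places the detail of cohort 3 adjustments in source documents, so check that each one also reaches the eCRF. Expect a few more table rows and some less favourable percentages.

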14.3 Efficacy and Pharmacodynamics Analyses

14.3.1 Analysis of Efficacy Endpoints

The numbers of patients with target ACT achieved before/during PCI and PCI success, or failed to finish PCI, or achieved ACT \geq 200 sec will be summarized by cohort and overall. The PA measurement will also be summarized descriptively by visit, cohort, and overall.

14.3.2 Analysis of Pharmacodynamic Endpoints

The ACT, aPTT, PT, TT, FIB, INR will be summarized descriptively by visit, cohort, and overall.

14.4 Safety Analysis

All reported AEs will be coded using the Medical Dictionary for Regulatory Activities (MedDRA), version used will be the current one at the time of analysis. The incidence of TEAEs

This document is confidential.

(events with onset dates on or after the start of the study drug) will be included in incidence summary tables. Events with missing onset dates will be included as treatment-emergent. If a patient experiences more than 1 occurrence of the same AE, the occurrence with the greatest severity and the closest association with the study drug will be used in the summary tables. The major bleeding events, minor bleeding events, MACE within 30 days, and AEs of interest will be summarized by MedDRA system organ class and preferred term, and by cohort and overall; SAEs and AEs causing study discontinuation will also be summarized. All AEs will be listed by patient, along with information regarding onset, duration, relationship and severity to study drug, action taken with study drug, treatment of event, and outcome.

Clinical laboratory data and vital signs will be summarized using descriptive statistics, including mean values and mean change from baseline values, as well as numbers of patients with values outside limits of the normal range at each time point.

12-lead ECGs will be summarized descriptively. The noteworthy QTcF interval (>450 , >480 , >500 msec) and noteworthy change from baseline (>30 and >60 msec) will also be summarized.

Summary tables will be provided for concomitant medications initiated during the study period.

Physical examination results will be listed.

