- Administer study drug via IV access before the PCI and record time of dosing in the eCRF. Study drug should be administered in catheterization lab as close to randomization and the start of the PCI procedure as possible.
- Conduct a visual bleeding inspection and assess bleeding AEs according to the BARC criteria; record any patient-reported bleeding.
- Record any other AEs that have occurred.

9.2.3 During Percutaneous Coronary Intervention, Day 1

Either radial access/distal radial access PCI or femoral access PCI will be used in this study. It is up to the discretion of the Principal Investigator what type of stent(s) will be used.

- Conduct the PCI procedure per local standard of care.
- Record TIMI flow grade post PCI.
- Patients who fail to achieve ACT target of 200 to 300 sec with MT1002 (within 30 minutes after MT1002 infusion initiation) before PCI will be switched to standard of care (UFH or bivalirudin, see Section 8.5.1).
- Patients who achieve ACT target of 200 to 300 sec with MT1002 (within 30 minutes after MT1002 infusion initiation) before PCI should continue the study drug infusion for 4 ± 0.5 hours after infusion start.
- Monitor patients for potential AEs, including allergic reactions during the MT1002 administration.
- Record vital signs (body temperature, respiration rate, heart rate, and systolic and diastolic blood pressure).
- Record any procedural complications, as well as any other AEs
 - Glycoprotein IIb/IIIa inhibitors may be used for procedural or angiographic complications only (dosing per local standard of care, see Section 8.5.1)
 - In those patients who experience significant intracoronary thrombosis during the procedure, or experience acute thrombosis after the procedure, heparin bail out may be administered (see Section 8.5.1).
- Perform a PA (by PFA100 or PFA200) according to the time points in the Schedule of Assessments (Table 4) and Table 5.

- Obtain central cardiac biomarkers (troponin I [troponin T can be measured if the local site does not have the troponin I test], and CK-MB) according to the time points in the Schedule of Assessments (Table 4) and Table 5.
- Obtain coagulogram (ACT, aPTT, PT, TT, FIB, INR according to the time points in the Schedule of Assessments [Table 4] and Table 5), hemoglobin, hematocrit, platelet count, RBC, and WBC counts.
- Obtain PK samples according to the time points in the Schedule of Assessments (Table 4) and Table 5.

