11.6 Adverse Events

11.6.1 Adverse Events

An AE is any symptom, physical sign, syndrome, or disease that either emerges during the study or, if present at Screening, worsens during the study, regardless of the suspected cause of the event. All medical and psychiatric conditions (except those related to the indication under study)

present at Screening will be documented in the medical history eCRF. Changes in these conditions and new symptoms, physical signs, syndromes, or diseases should be noted on the AE eCRF during the rest of the study. Clinically significant laboratory abnormalities should also be recorded as AEs.

Anticipated AEs

Anticipated AEs for this study population based on the results from the completed Phase 1 healthy volunteer study include bleeding (see also Section 11.6.3), allergic reactions, and headache.

Drug-related AEs which occurred in the completed Phase 1 study included headache, dizziness, discolored feces, mouth hemorrhage, injection site bruising and injection site nodule, and injection site hemorrhage.

Reporting of AEs

Patients will be instructed to report AEs at each study visit. All AEs are to be followed up until resolution or a stable clinical endpoint is reached.

Each AE is to be documented on the eCRF with reference to date of onset, duration, frequency, severity, relationship to study drug, action taken with study drug, treatment of event, and outcome. Furthermore, each AE is to be classified as being serious or nonserious. Changes in AEs and resolution dates are to be documented on the eCRF.

For the purposes of this study, the period of observation for collection of AEs extends from the time the patient gives informed consent until the end of study visit. Follow-up of the AE, even after the date of study drug completion, is required if the AE persists until the event resolves or stabilizes at a level acceptable to the Investigator.

When changes in the intensity of an AE occur more frequently than once a day, the maximum intensity for the event should be noted. If the intensity category changes over a number of days, then those changes should be recorded separately (with distinct onset dates).

Specific guidelines for classifying AEs by intensity and relationship to study drug are given in Table 7 and Table 8.

Table 7 Classification of Adverse Events by Intensity

Severity	Description

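### TEAEs are defined by onset date alone, so Day 1 events before the bolus, and post-consent events that ease after dosing, count as treatment-emergent

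*Combined protocol and SAP*

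**What the plan says.** - **TEAE definition (Section 14.4).** The TEAE tables take "events with onset dates on or after the start of the study drug) will be included in incidence summary tables". Events with no onset date are counted as treatment-emergent. There is no clock time and no condition about worsening after dosing.
- **What is collected (Section 11.6.1).** "Each AE is to be documented on the eCRF with reference to date of onset, duration, frequency, severity" and further items follow; onset time is not among them. The collection period "extends from the time the patient gives informed consent until the end of study visit", so it includes a stretch before dosing.
- **Changes of intensity (Section 11.6.1).** Within a day: "When changes in the intensity of an AE occur more frequently than once a day, the maximum intensity for the event should be noted". Across days: "If the intensity category changes over a number of days, then those changes should be recorded separately (with distinct onset dates". The direction of change is not restricted.
- **Dosing (Sections 8.2, 8.4 and 9.2.2).** "MT1002 should be initiated during diagnostics angiography when indication for PCI is confirmed". Staff must "record time of dosing in the eCRF", so the clock time of the bolus is known.
- **Conditions before dosing (Section 11.1).** Additional conditions present at consent or arising up to dosing are treated as concomitant, and only their worsening is an AE.

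**The concern.** The bolus time is recorded but the listed AE data give only a calendar date, so on Day 1 the two cannot be put in order. That day matters here. Arterial access and contrast come before MT1002, and intravenous heparin may run until enrollment. The pre-PCI visit in Section 9.2.2 already asks for bleeding and other AEs. An access-site bleed or contrast reaction before the bolus resembles the bleeding and hypersensitivity events that the trial watches for.

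The intensity rule adds a second route. An AE that starts after consent and before dosing, then eases on a later day after dosing, receives a new record with a post-dose onset date. An improvement then qualifies as a new event on treatment.

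The primary objective is a safe and well tolerated dose, cohorts hold six patients, and there is no control arm to show the background of procedural events. TEAE incidence would mix events caused by the procedure or earlier treatment with events that could be due to MT1002.

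**Working it through.** The plan gives no AE rate to reproduce. The only derived figure in its statistics section, 30 patients screened, follows from 18/(1 − 0.40) = 30 and does not bear on this point.

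**Step 1: apply the rule to hypothetical records.** Take the bolus at 11:00 on Day 1. The date rule is Section 14.4 with Section 11.6.1 recording. The comparison rule requires onset at or after the bolus and, for an intensity-change record, a rise in intensity.

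| Record | Date rule | Time-and-worsening rule |
|---|---|---|
| A. Access-site bleed, Day 1, 10:30 | TEAE | not TEAE |
| B. Severe AE starting after consent, day before dosing | not TEAE | not TEAE |
| B2. Same AE falls to mild on Day 2 (new record) | TEAE | not TEAE |
| C. Mild AE starting after consent, day before dosing | not TEAE | not TEAE |
| C2. Same AE worsens to moderate on Day 2 | TEAE | TEAE |
| D. New AE on Day 2 | TEAE | TEAE |
| E. Onset date missing | TEAE | TEAE (default kept) |

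The rules differ only on A and B2, both of which preceded the drug. An onset time alone would correct A but not B2, whose new record really is dated after dosing. A worsening condition alone would correct B2 but not A. Both changes are needed.

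**Step 2: size per affected patient.** Inputs are 6 patients per cohort (Section 6.1) and up to 18 in total (Section 14.1). The change is 1/n for a patient with no genuine TEAE in the row concerned; intervals are exact (Clopper-Pearson) 95%.

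| n | 0 affected | 1 affected | Change |
|---|---|---|---|
| 6 | 0% (0 to 45.9) | 1/6 = 16.7% (0.4 to 64.1) | 16.7 points |
| 18 | 0% (0 to 18.5) | 1/18 = 5.6% (0.1 to 27.3) | 5.6 points |

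Table 3 allows up to 8 patients in the third cohort; there the step is 1/8 = 12.5 points.

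**Step 3: compare the sections.** Section 11.1 uses the time of dosing as its boundary and makes only worsening an AE. Sections 9.2.1, 9.2.2 and 11.6.1 record events from consent as AEs, and Section 14.4 then sorts them by date. These sections do not give the same answer for an event between consent and bolus.

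**The case against.** The strongest reply is that the effect is narrow, conservative and open to correction.

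- **Direction.** The error over-reports harm in a descriptive single-arm trial, as the missing-date rule does by choice. That is a fair default for times nobody knows. It is no reason to discard times that could be known.
- **Other safeguards.** Every AE has a causality grade that considers temporal sequence, all AEs are listed by patient, and bleeding is assessed before, during and after PCI. With 18 patients the listings can be read by hand. These help interpretation but do not change the TEAE tables, and the pre-PCI visit is also where MT1002 starts, so the visit label does not settle the order.
- **The SAP.** Section 14 lets the SAP define variables and override the protocol, and no SAP text is available here. It could add a worsening clause; it could not recover an onset time that was never collected.

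A reader might infer more than the documents support:

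- **That any pre-existing condition that improves becomes a TEAE.** Sections 11.1 and 11.6.1 make a condition present at Screening an AE only if it worsens. One sentence in Section 11.6.1 speaks loosely of *changes* but does not displace that definition.
- **That a bleed resolving from severe through moderate to mild triples the count.** Section 14.4 tabulates one occurrence per patient, at greatest severity, and specifies no event-count table. It does not say whether intensity records are occurrences or whether this rule precedes the TEAE filter, which is an ambiguity and not shown inflation. Same-day changes create no new record.
- **That dose decisions or the bleeding co-primary endpoint are contaminated.** Table 1 does not use TEAE status. The Section 14.4 sentence on major bleeding and AEs of interest states no TEAE filter. Active bleeding is an exclusion and eligibility is rechecked before PCI, so a BARC 3–5 event before the bolus in a patient who is then dosed is unlikely.
- **That a known share of patients is affected.** An assumed 5% to 20% per patient would give a 1 − 0.95^6 = 26% to 1 − 0.80^6 = 74% chance of at least one in a cohort of six, but nothing in the documents supports either rate.

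**Conclusion.** The point holds for two kinds of event: AEs on Day 1 before the bolus, and AEs that begin between consent and dosing and ease on a later post-dose day. Both meet the stated TEAE definition although they preceded MT1002. The size is that given in Step 2 for each affected patient; the total is unknown.

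This rests on three assumptions: onset is compared with dosing by date, as the text says, although the start of study drug could be read as a clock time; the AE items in Section 11.6.1 are the full set, with no onset-time field on the eCRF; and no later SAP text changes the rule. If the eCRF already holds an onset time, only wording is needed. It is a modest point, worth correcting because the data field must exist while patients are being treated.

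**What to change.** 1. Record the clock time of onset for AEs on Day 1.
2. Define a TEAE as an event with onset date and time at or after the start of the MT1002 bolus, or a worsening in intensity after it. Unknown times may still default to treatment-emergent.
3. Link each intensity-change record to its parent event, so that a decrease is never a new TEAE, and state how the one-occurrence rule treats linked records.
4. Apply the same bolus-start boundary when tabulating BARC 3–5 bleeding and AEs of interest, for which no counting start is stated.
5. Reconcile Section 11.1 with Sections 9.2.1, 9.2.2, 11.6.1 and 14.4 on events between consent and dosing.

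The cost is one eCRF field and some SAP wording, with no extra procedures for patients.
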